8.2.5.2. Exposure-QTc Analysis

Linear mixed effect modeling to quantify the relationship between plasma concentrations of PF-04449913 and QTc interval will be performed. Additionally, the adequacy of the model fit to the assumption of linearity and the impact on quantifying the concentration response relationship will be explored including diagnostic evaluation. CCI [REDACTED]

The exposure-QTc analyses will be reported in a separate document. Data may be pooled with data from other studies and/or explored further with a PK/PD model.

The QTc-concentration analysis set will be used.

CCI [REDACTED]

CCI

[REDACTED]

[REDACTED]

[REDACTED]

[REDACTED]

[REDACTED]

CCI

[REDACTED]

[REDACTED]

[REDACTED]

[REDACTED]

CCI [Redacted]

[Redacted]

CCI [Redacted]

[Redacted]

[Redacted]

CCI [Redacted]

CCI

10. APPENDICES

Appendix 1. Categorical Classes for ECG and Vital Signs

Categories for QTcB and QTcF

QTcB/QTcF (ms)	max. < 450	450 ≤ max. < 480	480 ≤ max. < 500	max. ≥ 500
QTcB/QTcF (ms) increase from baseline	max. < 30	30 ≤ max. < 60	max. ≥ 60	

Categories for PR and QRS

PR (ms)	max ≥ 300	
PR (ms) increase from baseline	Baseline > 200 and max. ≥ 25% increase	Baseline ≤ 200 and max. ≥ 50% increase
QRS (ms)	max ≥ 200	
QRS (ms) increase from baseline	Baseline > 100 and max. ≥ 25% increase	Baseline ≤ 100 and max. ≥ 50% increase

Categories for Vital Signs

Systolic BP (mm Hg)	min. < 90	
Systolic BP (mm Hg) change from baseline	max. decrease ≥ 30	max. increase ≥ 30
Diastolic BP (mm Hg)	min. < 50	
Diastolic BP (mm Hg) change from baseline	max. decrease ≥ 20	max. increase ≥ 20
Supine pulse rate (bpm)	min. < 40	max. > 120

- Measurements that fulfill these criteria are to be listed in Appendix A of the study report.

Appendix 2. IWG Criteria: Response Criteria and Progression Definitions for Myelodysplasia***

Response Criteria (responses CR, PR, mCR must last at least 4 weeks)	Peripheral Blood				Bone Marrow Blasts (BMB) (%)	Other
	Hgb(g/dL)	Neutrophils (L)	Platelets (L)	Blasts (%)		
Complete Remission (CR)**	≥11	≥1 x 10 ⁹	≥100 x 10 ⁹	0	≤5	Normal maturation of all cell lines, note if has persistent dysplasia
Partial Remission (PR)**					Decreased by ≥50% but still >5%	All CR criteria if abnormal before treatment except BMB
Marrow CR (mCR)	If hematologic improvement (HI) response, note in addition to Marrow CR				≤5% & decreased by ≥50%	
Stable Disease*						Failure to achieve PR & no evidence of progression*
Failure						Death, or disease progression: worsening cytopenia, increase in % BM blasts, progression to a more advanced MDS FAB subtype
Relapse after (m)CR or PR					ICH	At least one of the following: Return to pre-treatment BMB % Decrement of ≥50% from maximum remission/response levels in granulocytes or platelets Reduction in Hgb ≥1.5g/dL or transfusion dependence

Additional Response Criteria for Myelodysplasia

Cytogenetic Response	
Complete	Disappearance of chromosomal abnormality with no appearance of new ones
Partial	≥50% reduction of chromosomal abnormality
Disease Progression For patients with % blasts at screening: <5% bone marrow blasts 5-10% bone marrow blasts 11-20% bone marrow blasts 21-30% bone marrow blasts	≥50% increase to >5% bone marrow blasts ≥50% increase to >10% bone marrow blasts ≥50% increase to >20% bone marrow blasts ≥50% increase to >30% bone marrow blasts
For all categories, any of:	At least 50% decrease from maximum remission/response in granulocytes or platelets Reduction in Hgb by ≥2 g/dL Transfusion dependence

Proposed modified IWG Myelodysplasia Response Criteria for Hematologic Improvement (HI)**

Erythroid response (pre-treatment <11g/dL)*	Hgb increase by ≥1.5 g/dL Relevant reduction of units of RBC transfusions by an absolute number of at least 4 RBC transfusions/8 weeks as compared to the pretreatment transfusion number in the previous 8 weeks (only RBC transfusions given for Hb ≤9 g/dL pretreatment will count in the RBC transfusion evaluation).
Platelet Response (pretreatment <100 x10 ⁹ /L)*	Absolute increase of ≥30 x10 ⁹ /L if starting with >20 x 10 ⁹ /L platelets Increase from <20 x 10 ⁹ /L to >20 x10 ⁹ /L and by at least 100%
Neutrophil Response (pretreatment <1 x 10 ⁹ /L)*	At least a 100% increase and an absolute increase >0.5 x10 ⁹ /L
Progression or relapse after HI in the absence of another explanation	At least one of the following: 
 • At least 50% decrease from maximum response levels in granulocytes or platelets; • Reduction in Hgb by ≥1.5g/dL; • Transfusion dependence.

*Pretreatment counts averages of at least 2 measurements (not influenced by transfusions) ≥1 week apart.

** Hematologic Improvement must last ≥ 8 weeks and is derived based on lab data entered in the database.

***This criteria will be applied also to patients with oligoblastic AML and CMML without proliferative disorder.

Appendix 3. IPSS-R Classification System for Myelodysplastic Syndromes*

Prognostic variable	0	0.5	1	1.5	2	3	4
Cytogenetics	Very Good		Good		Intermediate	Poor	Very Poor
Bone Marrow Blast %	≤2		>2 to <5		5-10	>10	
Hemoglobin	≥10		8 to <10	<8			
Platelets	≥100	50-<100	<50				
ANC	≥0.8	<0.8					
Risk Category				Risk Score			
Very Low				≤1.5			
Low				>1.5-3			
Intermediate				>3-4.5			
High				>4.5-6			
Very High				>6			

Adapted from Greenberg PL, Bennett JM et al. Clinical application and proposal for modification of the international working group (IWG) response criteria in myelodysplasia. Blood 2006; 108(2) 419-25.

*Only applies to MDS patients enrolled in the Expansion component of the study.

Appendix 4. 2017 ELN Response Criteria for Acute Myeloid Leukemia

Response Criteria	Neutrophils (μL)	Platelets (μL)	Bone Marrow Blasts (%)	Other
Complete Remission without Minimal Residual Disease (CR_{MRD})				Assessed in CR and CRi patients only by central multiparameter flow cytometry
Morphologic Complete Response (CR)	$\geq 1,000$	$\geq 100,000$	<5 with spicules; no peripheral blasts, no blasts with Auer rods	Transfusion independent, no EMD
Complete Remission with partial hematologic recovery (CRh)¹	>500	>50,000 □	<5; no peripheral blasts; no blasts with Auer rods	No EMD; Not qualifying for CR
Morphologic CR with incomplete blood count recovery (CRi)	<1,000 -or-	<100,000	<5	Either neutrophils or platelets not recovered, no EMD
Morphologic leukemia-free state (MLFS)	<1,000 -and-	<100,000	<5 with spicules and no blasts with Auer rods	Neutrophils and platelets not recovered, Flow cytometry negative, no EMD
Partial remission (PR)	$\geq 1,000$	$\geq 100,000$	decrease to 5-25 blasts and $\geq 50\%$ decrease from pretreatment	Blasts $\leq 5\%$ if Auer rod positive
Stable Disease (SD)				Absence of CR _{MRD} , CR, CRi, PR, MLFS and criteria for PD not met. Should last at least 3 months.

Progressive Disease (PD)
			
>50% increase in blasts from pretreatment (if baseline is <30% blasts, must have at least 15% increase; or >70% blasts for ≥3 months; no improvement in ANC (>0.5 x 10⁹/L [500 μL], and/or platelet count to >50 x 10⁹/L [50 000 μL nontransfused]; or > 50% increase in peripheral blasts (WBC count x % blasts) to >25 x 10⁹/L (25000 μL); or new EMD
	
--	--	--	--	--

ANC=Absolute neutrophil count; WBC=white blood cell; EMD=extramedullary disease.

There is no minimum requirement for bone marrow cellularity or hemoglobin concentration for response criteria.

Composite from Cheson, BD, Bennett JM, Kopecky KJ, et al. Revised recommendations of the International Working group for diagnosis, standardization of response criteria, treatment on outcomes and reporting standards for therapeutic trials in acute myeloid leukemia. J Clin Oncol 2003; 21(24):4642-4649 and Döhner H, Estey E, Grimwade D, et al. Diagnosis and management of AML in adults: 2017 ELN recommendations from an international expert panel. Blood 2017;129(4): 424-47.²

¹CRh is not part of the 2017 ELN recommendations, but is a required assessment for this study.

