		
 • Removed requirement that disease assessments be done >3 weeks from dosing of G-CSF or GM-CSF (also sections 5.7.4, 7.7.3, and 9.3.6). 
Section 1.2.20: Summary of glasdegib TQT study added.
 
Sections 1.2.3 and 4.1.2: Added eligibility of CMML patients and MDS/MPN, unclassifiable patients, for the MDS cohort.
 
Section 1.2.16: Updated toxicities reported for azacitidine.
 
Sections 1.2.16.2, 5.4.5 and 5.7.4: Replaced all azacitidine dose modification criteria with reference to local label, Investigational Product Manual, or SPC.
 
Throughout sections applicable to expansion cohorts: Clarified azacitidine dosing is to be done per local label, Investigational Product Manual, or SPC.
 
Section 4.1.2: Revised definition of adequate organ function (inclusion criterion #4).
 
Section 4.2.2.: Removed exclusion criterion for patients with HBV, HCV, HIV or AIDS related illness.
 
Section 4.2.2: Revised cardiac exclusion criteria.
 
Section 5.2: Restricted requirement for azacitidine dosage Preparation Record to cases where Pfizer is providing azacitidine.
 
Section 5.4.5: Revised glasdegib dose modification.
 
Sections 5.7.1 and 7.6: Removed requirement for additional ECGs when moderate/strong CYP3A4/5 inhibitor or drug with TdP risk is initiated.

Document	Version Date	Summary of Changes
		
Section 5.7: Revised allowed and restricted concomitant medications.
 
Section 8.6.2: Added definition of confirmed Hy's law case.
 
Section 13: Defined end of trial as last patient last visit for all countries.
 
Appendices 3, 10, 16: Corrected literature references.
 
Appendix 4: Added list of moderate CYP3A4/5 inducers.
 
Appendix 8: Edited description of urinalysis.
 
Appendix 11: Added descriptions of additional AML response categories.
 
Appendix 18: Added France-specific appendix.
 
Replaced PF-04449913 with glasdegib throughout.
 
Abbreviation list updated.
 
Table of Contents updated.
 
General spelling, grammar, and consistency issues corrected throughout the protocol.

This amendment incorporates all revisions to date, including amendments made at the request of country health authorities, institutional review boards/ethics committees (IRBs/ECs), etc.

Abbreviations

Abbreviation	Term
7 + 3	Induction Chemotherapy with Cytarabine (7 days) plus Daunorubicin (3 days)
AE	Adverse Event

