9. DATA ANALYSIS/STATISTICAL METHODS

A detailed methodology for summary and statistical analysis of the data collected in this study will be documented in a Statistical Analysis Plan will be maintained by the Sponsor. The document may modify the plans outlined in the protocol; however, any major modifications of the primary endpoint definition and/or its analysis will also be reflected in a protocol amendment.

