Appendix 11. 2017 ELN Response Criteria for Acute Myeloid Leukemia

Response Criteria	Neutrophils (μL)	Platelets (μL)	Bone Marrow Blasts (%)	Other
Complete Remission without Minimal Residual Disease (CR_{M RD})				If studied pretreatment, CR with negativity for a genetic marker by RT qPCR, or CR with negativity by multiparameter flow cytometry
Morphologic Complete Response (CR)	$\geq 1,000$	$\geq 100,000$	<5; no peripheral blasts; no blasts with Auer rods	No EMD; Transfusion independent
Complete Remission with partial hematologic recovery (CRh)¹	>500	>50,000	<5; no peripheral blasts; no blasts with Auer rods	No EMD; Not qualifying for CR
Morphologic CR with incomplete blood count recovery (CRi)	<1,000 -or-	<100,000	<5; no peripheral blasts; no blasts with Auer rods	No EMD; Either neutrophils or platelets not recovered; Not qualifying for CRh
Morphologic leukemia-free state (MLFS)	<1,000 -and-	<100,000	<5; no blasts with Auer rods	No EMD; Neutrophils and platelets not recovered; BM not merely “aplastic”; BM cellularity must be 10%, or 200 cells enumerated; Not qualifying for CRi
Partial remission (PR)	$\geq 1,000$	$\geq 100,000$	blasts decrease to 5-25 and $\geq 50\%$ decrease from pretreatment	Blasts $\leq 5\%$ if Auer rod positive
Stable Disease (SD)				Absence of CR _{M RD} , CR, CRh, CRi, PR, MLFS and criteria for PD not met. Should last at least 3 months.

Progressive Disease (PD)			>50% increase in blasts from pretreatment (if baseline is <30% blasts, must have at least 15% increase; or >70% blasts for ≥3 months; no improvement in ANC (>0.5 x 10 ⁹ /L [500 μL], and/or platelet count to >50 x 10 ⁹ /L [50 000 μL nontransfused]); or > 50% increase in peripheral blasts (WBC count x % blasts) to >25 x 10 ⁹ /L (25000 μL); or new EMD
Relapse			
Hematologic relapse (after CRMRD-, CR, CRi)			Bone marrow blasts >5%; or Reappearance of blasts in the blood; or Development of EMD
Molecular Relapse (after CRMRD-)			If studied pretreatment, reoccurrence of MRD as assessed by RT-qPCR or multiparameter flow cytometry
Treatment Failure			
Primary refractory disease	For Non Intensive: Treatment Failure is defined as failure to achieve CR or CRh following up to 6 cycles of study treatment.		
Death in aplasia	Deaths occurring ≥7 days following completion of initial treatment while cytopenic; with an aplastic or hypoplastic bone marrow obtained within 7 days of death, without evidence of persistent leukemia.		

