1. AMENDMENTS FROM PREVIOUS VERSION(S)

This amendment of the Statistical Analysis Plan was finalized following Protocol Amendment #5 dated August 22, 2017 and Amendment #6 dated Nov 27, 2017. The main changes relevant to this analysis plan are as follows:

Randomized Phase 2 component is removed from the protocol in amendment #5. Expansion component with two cohorts, MDS and AML, are added into the protocol. Bayesian decision rule is used in the expansion component of the study for potential early stopping.

In amendment 6, a set of safety stopping criteria are added. CRh as one of the secondary endpoints for AML patients. CCI as exploratory endpoints are added. PRO endpoint PGIS has been updated from a 7-point Likert scale to a 4-point Likert scale. All of these additions and changes were per FDA request.

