2.1.2. Expansion

Patients with previously untreated Intermediate, High, or Very High risk MDS per IPSS-R (n=30) or patients with AML who are not candidates for intensive chemotherapy (n=30) will receive PF-04449913 100 mg orally once/day in combination with azacitidine 75 mg/m²/day given by SC or IV for 7 days (±3 days) every 28 days.

Figure 1. Schematic of Study Design

*MDS patients enrolled in the Safety Lead-In component must have Intermediate-2 or High-Risk disease according to IPSS.

**MDS patients enrolled in the Expansion component must have Intermediate, High, or Very High risk disease according to IPSS-R.

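### Protocol Appendix 11 and SAP Appendix 4 give conflicting criteria for AML complete remission without minimal residual disease

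*SAP*

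**What the plan says.** Both documents carry a table of 2017 ELN response criteria for AML, and both tables open with a row for CR MRD-.

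Protocol Appendix 11 defines it as "If studied pretreatment, CR with negativity for a genetic marker by RT qPCR, or CR with negativity by multiparameter flow cytometry". The patient must be in CR, either assay will serve, and no laboratory is named. The molecular relapse row of the same appendix uses the same two assays: "If studied pretreatment, reoccurrence of MRD as assessed by RT-qPCR or multiparameter flow cytometry".

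SAP Appendix 4 fills the row with "Assessed in CR and CRi patients only by central multiparameter flow cytometry". It brings in CRi patients and central reading. It leaves out RT-qPCR and the pretreatment condition.

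CRi is a category of its own, separate from CR, in both tables. The protocol describes it as "Either neutrophils or platelets not recovered; Not qualifying for CRh".

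SAP Section 1 says that the SAP was "finalized following Protocol Amendment #5 dated August 22, 2017 and Amendment #6 dated Nov 27, 2017". The visible part of its list of changes does not mention the MRD definition.

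**The concern.** Two rows with one label should identify the same patients. Here, someone deriving the category from the SAP and someone reading the protocol would not arrive at the same set.

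CR MRD- is naturally read as depth of remission: of the patients in CR, how many also have no detectable residual disease. That reading holds only if the category lies inside CR, which is the primary endpoint of the expansion. If CRi patients are included, the category can contain patients who are not responders on the primary endpoint. In the protocol the label also fixes who can later have a molecular relapse.

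The row is unlikely to be idle. The protocol's schedule for the expansion (Table 3, footnote 16) refers to marrow samples collected for MRD assessment.

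**Working it through.** The plan states no figure for this category, so there is none to reproduce. The check compares the two rows and then sorts patients by them.

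**Step 1. The rows side by side.**

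| Element | Protocol Appendix 11 | SAP Appendix 4 |
|---|---|---|
| Responders | CR | CR and CRi |
| Assay | RT-qPCR or multiparameter flow | Multiparameter flow |
| Reading | Not stated | Central |
| Studied pretreatment | Required, at least for RT-qPCR | Not mentioned |

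The word *only* in the SAP row could attach to the patients or to the method. On either reading, flow is the sole method listed and CRi patients are included.

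**Step 2. Who is classified differently.**

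| Patient | Protocol row | SAP row |
|---|---|---|
| A. CR, studied pretreatment, RT-qPCR-negative, central flow positive or missing | Meets it | Cannot meet it |
| B. CRi, central flow negative | Cannot meet it | In the assessed population; the label is implied by the row title, not stated |
| C. CR, central flow negative, not studied pretreatment | Depends on whether the condition covers the flow clause | Can meet it |
| D. CR, central flow negative, studied pretreatment | Meets it | Meets it |

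**Step 3. Size.** Let a, b and c be the numbers of patients of types A, B and C who are counted by one document and not the other. Then:

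SAP count − protocol count = b + c − a

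Here b is 0 if the SAP label is in fact reserved for CR, and c is 0 if the pretreatment condition covers RT-qPCR alone. The documents give none of the three numbers, so the sign is undetermined.

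The AML cohort is planned at 30 (SAP 2.1.2), and each such patient moves the proportion by 1/30 = 0.033, or 3.3 percentage points:

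- b + c − a = +1: SAP proportion higher by 3.3 points.
- b + c − a = 0: equal proportions, possibly made up of different patients.
- b + c − a = −1: SAP proportion lower by 3.3 points.

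**Step 4. The edge of CRi.** The protocol's CRi excludes patients who qualify for CRh; the SAP's CRi row has no such exclusion. In the SAP table, a patient with neutrophils above 500 but below 1,000 and platelets of at least 100,000 meets the count limits of both rows. Whether CRh patients enter the SAP's MRD population is therefore also open.

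**The case against.** **The SAP row concerns assessment, not labelling.** It says in whom and how MRD is assessed. It gives no criterion for negativity, and CRi keeps its own row. Testing CR and CRi patients while labelling only CR patients would fit the text. This stands: that CRi patients become CR MRD- is implied by the row title and not stated. It does not touch type A, because the SAP row gives RT-qPCR no role.

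**The SAP may depart from the protocol.** Protocol Section 9 says "The document may modify the plans outlined in the protocol", and only major changes to the primary endpoint need an amendment. So the SAP is entitled to differ. The visible text does not say that a different definition was intended.

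**Version lag.** The SAP follows Amendments 5 and 6. The protocol's history for Amendment 7 (14 June 2018) records "Appendix 11: Added descriptions of additional AML response categories". That may explain the mismatch, but it does not tell an analyst which row to use.

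**Redaction.** CR MRD- is not among the visible primary or secondary endpoints, and exploratory text is blacked out in both documents, including an item in the SAP's list of changes. The population and assay may be settled there. This stands, and it limits the point to the two visible tables.

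**Molecular CR.** SAP 6.1.2.1.1 lists a separate molecular complete response, which might capture RT-qPCR results. Neither response table has a row defining it, so it does not fill the gap.

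**Conclusion.** The two rows conflict on eligible responders, assay, reading and pretreatment condition, and no visible text reconciles them. Type A is the firm discrepancy. Type B is probable, so the SAP category may not be a subset of CR. The size is 3.3 percentage points per reclassified patient if 30 are enrolled, in an unknown net direction.

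Three stronger readings are tempting, and the documents do not support them:

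- *The SAP inflates the rate.* Assume 8 CR and 3 CRi patients, with 40% flow-negative in each group. Counting only the CRi effect gives 0.4 × 8 = 3.2 (3.2/30 = 11%) under the protocol and 0.4 × 11 = 4.4 (4.4/30 = 15%) under the SAP. These counts are assumed, and the sum leaves out type A. An average of 4.4 − 3.2 = 1.2 type A patients would cancel the rise.
- *The primary result is at risk.* The CR rate rests on its own row, and the futility rule uses CR. Neither depends on MRD.
- *A CR patient who is flow-negative but RT-qPCR-positive is a further discrepancy.* With pretreatment study done, such a patient meets both rows. Whether that is sensible is a question about the protocol's own definition, not a difference between the documents.

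This is a minor point, worth settling before the category is derived.

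**What to change.** Use one definition in both tables:

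- State that CR MRD- requires CR as defined in protocol Appendix 11.
- Name the same assay or assays, central or local reading, and pretreatment condition in both documents, and say whether that condition applies to flow.
- Report MRD-negative CRi, and CRh if it is assessed, on a separate line.
- Keep the FAS as denominator, as for the AML response proportions in SAP 8.2.2.2.2. Following the SAP 7.2 rule for response, count patients not known to be MRD-negative as not achieving the category.
- A proportion among CR patients with an evaluable sample may be added as a supplement. It should not replace the FAS figure: on the assumed counts above, and with all 8 CR patients evaluable, it would read 3.2/8 = 40% where the FAS figure is 11%.

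The cost is table wording only. The reported MRD-negative CR count may change slightly in either direction.

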9.3.6. Other Efficacy Measures

Additional efficacy measure of interest for the safety LIC and expansion MDS cohort include marrow CR (mCR), partial remission (PR), stable disease (SD), partial or complete cytogenetic response, and hematologic improvement (HI). Additional efficacy measures of interest for the expansion AML cohort include CR with incomplete hematologic recovery (CRi), complete remission with partial hematologic recovery (CRh), morphologic leukemia-free state (MLFS), PR, SD, Cytogenetic CR (CRc), and molecular CR (CRm) per [Appendix 11](#).

The proportion of patients ever achieving each of the endpoints for the respective cohort will be estimated with two-sided 95% CI respectively.

CCI
[Redacted text block]

CCI [REDACTED]

[REDACTED]

[REDACTED]

[REDACTED]

[REDACTED]

CCI [REDACTED]

[REDACTED]

[REDACTED]

CCI [REDACTED]

[REDACTED]

CCI [REDACTED]

[REDACTED]

CCI

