8.2.2.2.2. Other Efficacy Measures

Specifically, for AML cohort, the following binary efficacy endpoints (with 95% exact CI) will be summarized in frequency tables, proportion of patients achieving CR, CRh, CRi, CR/CRi, MLFS, PR, SD, CRc, , CRm, and CR+PR.

For MDS cohort, the following binary efficacy endpoints (with 95% exact CI) will be summarized in frequency tables, proportion of patients achieving CR, marrow CR, PR, SD, CR+PR, and Partial or Complete Cytogenetic Response, as well as the proportion of patients ever achieving HI.

The FAS will be used.

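### The SAP's AML response table lets one patient be both CRh and CRi, the protocol's table does not, and no readable text reconciles them

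*SAP*

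**What the plan says.** **Protocol Appendix 11.** The last column of the CRi row reads "No EMD; Either neutrophils or platelets not recovered; Not qualifying for CRh". Its marrow column also requires no peripheral blasts and no blasts with Auer rods. The SD row requires absence of "CR, CRh, CRi, PR, MLFS and criteria for PD not met", among other things.

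**SAP Appendix 4.** The CRi row has the same count thresholds (ANC below 1,000 or platelets below 100,000). Its marrow column gives only blasts below 5%, and its last column ends "platelets not recovered, no EMD". The CRh row has the same thresholds as the protocol (ANC above 500, platelets above 50,000) and excludes only CR: "No EMD; Not qualifying for CR". The SD row reads "CR, CRi, PR, MLFS and criteria for PD not met", so CRh is missing from the list.

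**Analyses.** SAP 8.2.2.2.2 plans, with exact 95% intervals, the "proportion of patients achieving CR, CRh, CRi, CR/CRi, MLFS, PR, SD" and further categories in the AML cohort. Protocol 9.3.6 says: "The proportion of patients ever achieving each of the endpoints for the respective cohort will be estimated". It lists CRi and CRh but not a CR/CRi composite.

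**Status of the two texts.** Protocol Section 9 allows the SAP to modify the planned analyses and requires an amendment only for major changes to the primary endpoint. SAP Section 1 states that it follows Protocol Amendments 5 and 6. On AML response its list of main changes mentions the addition of CRh and nothing about CRi.

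**The concern.** The same marrow and blood counts can fall into different sets of categories depending on which table is applied. The readable SAP has no ranking of categories or best-response rule that would remove the overlap. (Some SAP text on endpoints is redacted or missing, so this is limited to what can be read.) Two programmers, each following one table, could report different CRi and CR/CRi rates from one dataset, and a reader of the report could not tell whether a CRh patient had been counted once or twice.

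**Working it through.** The plan states no figure for CRi or CRh, so there is none to reproduce. The only related figure is the maximum exact 95% interval width of 0.374 at n = 30 (Protocol 9.1.2). It reproduces as 0.3741, but this point does not depend on it.

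**Step 1. Rules as written.** Take a patient with marrow blasts below 5%, no peripheral blasts, no Auer rods, no extramedullary disease and transfusion independence, and assume that each table's extra marrow or flow conditions for MLFS are met.

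- CR: ANC ≥1,000 and platelets ≥100,000 (both documents).
- CRh: ANC >500 and platelets >50,000, not CR (both documents).
- CRi: ANC <1,000 *or* platelets <100,000; the protocol adds not CRh.
- MLFS: ANC <1,000 *and* platelets <100,000; the protocol adds not CRi.

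The *or* in CRi can be read as exclusive (exactly one count unrecovered, as the contrast with MLFS suggests) or inclusive. Both were run.

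**Step 2. All nine count patterns.**

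| ANC | Platelets | Protocol, exclusive | SAP, exclusive | Protocol, inclusive | SAP, inclusive |
|---|---|---|---|---|---|
| ≤500 | ≤50,000 | MLFS | MLFS | CRi | CRi, MLFS |
| ≤500 | 50,001-99,999 | MLFS | MLFS | CRi | CRi, MLFS |
| ≤500 | ≥100,000 | CRi | CRi | CRi | CRi |
| 501-999 | ≤50,000 | MLFS | MLFS | CRi | CRi, MLFS |
| 501-999 | 50,001-99,999 | CRh, MLFS | CRh, MLFS | CRh, MLFS | CRh, CRi, MLFS |
| **501-999** | **≥100,000** | **CRh** | **CRh, CRi** | **CRh** | **CRh, CRi** |
| ≥1,000 | ≤50,000 | CRi | CRi | CRi | CRi |
| **≥1,000** | **50,001-99,999** | **CRh** | **CRh, CRi** | **CRh** | **CRh, CRi** |
| ≥1,000 | ≥100,000 | CR | CR | CR | CR |

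The two bold patterns move from CRh only to CRh and CRi on either reading. The boundary values (ANC 501 and 999 with platelets 100,000; ANC 1,000 with platelets 50,001 and 99,999) all show it. Under the inclusive reading the pattern with both counts partly recovered also gains CRi in the SAP.

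**Step 3. Who changes a rate.** Under the protocol's ever-achieving rule, a bold-pattern patient adds to the SAP's CRi count if no other assessment gives protocol CRi; a later CR does not cancel it. The same patient adds to CR/CRi only if CR is also never reached.

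**Step 4. Size.** The shift per such patient is 1/n. At n = 30 it is 1/30 = 3.3 points. If enrolment stopped early it would be larger; for an assumed n = 20 it is 1/20 = 5.0 points.

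As an illustration, assume 0/30 CRi under the protocol table and k extra patients under the SAP table. The Clopper-Pearson limits are the 2.5% quantile of Beta(k, 31−k) and the 97.5% quantile of Beta(k+1, 30−k):

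| k | Rate | Exact 95% CI |
|---|---|---|
| 0 | 0% | 0-11.6% |
| 1 | 3.3% | 0.1-17.2% |
| 2 | 6.7% | 0.8-22.1% |
| 3 | 10.0% | 2.1-26.5% |

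The values of k are assumptions; the documents give no basis for choosing one.

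**Step 5. The other omissions.** A patient with a marrow below 5% but peripheral blasts or Auer rods, and one count low, fits the SAP's CRi row but not the protocol's. In the SD row, the missing CRh makes no difference to the bold patterns at present, because the SAP already bars them from SD through CRi. If the CRh bar were added to CRi and the SD list left alone, those patients could meet both CRh and SD. The two rows must therefore be changed together.

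**The case against.** **The SAP table may not be the one applied.** The SAP's AML endpoint list (6.1.2) and 8.2.2.2.2 do not cite Appendix 4, whereas Protocol 2.4, 7.7.1 and 9.3.6 all tie the AML endpoints to Appendix 11. If sites classify response under Appendix 11, nothing changes. This stands. A reader might infer that the reported CRi rate will be inflated; the documents support only the conditional statement.

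**The SAP is allowed to differ.** This also stands. A reader might infer that the SAP breaches a governing table, but Protocol Section 9 gives that latitude for secondary endpoints, and no readable passage says which table prevails. Nor does the SAP's silence show much, because Section 1 lists main changes from its previous version, not departures from the protocol.

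**Version lag.** The amendment log credits Amendment 6 with adding CRh and clarifying how the categories relate, and the SAP says it follows that amendment. Its CRh row already carries the protocol's wording, which points to incomplete carry-over. But Amendment 7 edited Appendix 11 again, and the Amendment 6 table is not available, so lag cannot be excluded. Either cause leaves two texts to reconcile.

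**The SAP row may be deliberate.** Both documents note that CRh lies outside the 2017 ELN categories, so a CRi row without a CRh bar fits the table's title. Moreover, barring CRh from CRi makes CR/CRi odd: ANC 300 with platelets 150,000 would count, while ANC 700 with platelets 150,000 would not. This is a fair point and shapes the remedy.

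**Conclusion.** The conflict is real and can be verified by reading the two CRi rows together. Two count patterns are classified differently on either reading of *or*. If Appendix 4 is used and such patients occur, CRi and CR/CRi are higher than under Appendix 11 by 1/n per affected patient: about 3.3 points at 30, which is not an upper bound if the cohort is smaller. The number affected is unknown.

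The reach is limited. These are descriptive proportions (SAP 4.1 states no formal hypotheses), and CR/CRi is planned only in the SAP, so it contradicts no protocol rate. The CRi row does not enter the primary CR rate or the futility and safety rules. It should be fixed before the AML response tables are produced, but it does not threaten the trial's main conclusion.

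**What to change.** In the SAP, do one of two things.

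1. Align Appendix 4 with Appendix 11: exclude patients who qualify for CRh from CRi, add the peripheral-blast and Auer-rod conditions to CRi, and add CRh to the SD list, all in one change.
2. Keep the overlap and declare it in the SAP as an intended departure from Appendix 11.

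In either case, name the table used to classify AML response and state whether CR/CRi includes CRh patients. If CRi excludes CRh, report CR+CRh+CRi in place of or beside CR/CRi, so that patients with better count recovery are not lost from the composite.

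A separate minor point can be settled in the same edit. Neither table excludes CRh from MLFS (the protocol's MLFS row ends "BM cellularity must be 10%, or 200 cells enumerated; Not qualifying for CRi"), so a patient with both counts partly recovered can meet both. A ranking of categories in the SAP would resolve this without a protocol amendment.

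The cost is SAP wording and the matching programming; no new data are needed. Under the first option, CRi and CR/CRi may come out somewhat lower than the present SAP table would give.
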